## Phase 2: Zoledronic acid

### **Specific Aims:**

In Phase 2, participants will receive a single infusion of open-label zoledronic acid (an intravenous bisphosphonate) 5 mg after the initial 12-month administration of romosozumab or placebo. We hypothesize that 12 months of romosozumab followed by a single intravenous infusion of open-label zoledronic acid will result in a greater increase in BMD compared to 12 months of placebo followed by a single intravenous infusion of open-label zoledronic acid. Within the group of women who receive sequential therapy with 12 months of romosozumab followed by a single intravenous infusion of zoledronic acid, we hypothesize that BMD will be maintained between 12 and 24 months following administration of zoledronic acid.

**Specific Aim 1:** We hypothesize that 12 months of romosozumab followed by a single intravenous infusion of open-label zoledronic acid will result in a greater increase in BMD compared to 12 months of placebo followed by a single intravenous infusion of open-label zoledronic acid.

We will investigate whether sequential therapy of 12 months of romosozumab followed by a single intravenous infusion of open-label zoledronic acid results in a significantly greater increase in BMD from baseline to 24 months compared to 12 months of placebo followed by a single intravenous infusion of open-label zoledronic acid. The primary endpoint will be lumbar spine BMD at 24 months in the romosozumab/zoledronic acid group compared to the placebo/zoledronic acid group. BMD will be measured at baseline and 24 months.

**Specific Aim 2:** We hypothesize that within the group of women who receive sequential therapy with 12 months of romosozumab followed by a single intravenous infusion of open-label zoledronic acid, BMD will be maintained between 12 and 24 months following administration of zoledronic acid.

We will investigate whether a single intravenous infusion of open-label treatment with zoledronic acid will maintain the hypothesized gains in BMD achieved after 12 months of romosozumab administration. The primary endpoint will be lumbar spine BMD at 24 months. BMD will be measured at 12 and 24 months.

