7. Plain film of wrist/hand to determine bone age in women with primary amenorrhea who have not received estrogen for  $\geq 1$  year.
8. Electrocardiogram (ECG or EKG) to assess cardiovascular risk.

If the 25-OH vitamin D level at the screening visit is not  $>30$  ng/ml, participants will be given one loading dose of oral vitamin D3 (cholecalciferol) 5,000 IU daily and the 25-OH vitamin D level will be checked every 3 weeks until their 25-OH vitamin D level meets the eligibility requirement ( $>30$  ng/ml).

**Baseline Visit:** Eligible study subjects (n=30 women with anorexia nervosa or atypical anorexia) will be assessed at an outpatient visit at MGH for baseline testing.

1. A clinical and bionutrition evaluation and urine pregnancy test (unless exempt from urine hCG).
2. DXA scan of the spine, hip, radius, and total body for BMD and body composition, including lean mass, if screen visit did not take place within 6 weeks of baseline visit or if a DXA scan was not performed at the screening visit.
3. Baseline hormone and safety blood testing, if not performed clinically within 2 weeks prior to the baseline visit.
4. HR-pQCT and FEA of the radius and tibia
5. Eating Disorder Examination—Questionnaire
6. Eating Disorder Inventory-3
7. Paffenbarger Exercise Questionnaire
8. Calcium and vitamin D food frequency questionnaire

Randomization to treatment or placebo group will occur at the baseline visit. Twenty subjects will be randomized to active romosozumab (210 mg, which must be administered as two injections of 105 mg) and 10 subjects will be randomized to identical placebo injections. In the rare case that a subject withdraws from the study after being randomized but prior to completing the baseline visit, we will replace such dropouts with the goal that thirty subjects will complete the baseline visit. Randomization will be stratified for presence or absence of atypical anorexia nervosa, defined as  $BMI \geq 18.5$  kg/m^2 vs.  $< 18.5$  kg/m^2. Subjects will return every month over the following 12 months to receive ongoing injections.

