## VI. Biostatistical Analysis

**Sample Size and Justification:** Group sample sizes of 20 (active therapy) to 10 (placebo) for a total N=30 will achieve 80% power to reject the null hypothesis of equal means when the population mean difference is at least 9% with a standard deviation between groups of 8% and with a significance level of (alpha) of 0.050 using a 2-sided 2-sample equal-variance t-test. This is based on the difference in percent change in spine bone density between the romosozumab (n=65) and placebo (n=61) groups in Cosman F. *et al.*.

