### **Data Analysis Plan:**

The data analysis plan for the study will be as follows. The primary analysis will be intention-to-treat, with the primary endpoint being change in PA lumbar spine aBMD. Statistical significance will be defined as a two-tailed p-value of  $\leq 0.05$ .

Phase 1 Aims 1-3: Baseline mean clinical characteristics between the 2 groups will be compared by t-test. Variables will be tested for normality using the Shapiro-Wilk test, and if non-normal, variables will be log-transformed before analysis. If the distribution remains non-normal after log-transformation, nonparametric testing using the Wilcoxon rank sum test will be performed instead. The analysis of variables at 12 months will be performed using a linear random effects model to estimate and test the effects of the 2 randomization groups (romosozumab vs placebo) from baseline to 12 months on the study endpoints.

Phase 1 Aim 4: The analysis of variables at 12 months will be performed using a linear random effects model to estimate and test the effects of the 2 randomization groups (romosozumab vs placebo) from baseline to 12 months on the study endpoints. We will also add a lean body mass x randomization group interaction term to examine if the effects of body mass change differ between romosozumab and placebo.

Phase 2 Aim 1: The analysis of variables at 24 months will be performed using a linear random effects model to estimate and test the effects of the 2 randomization groups (12 months of romosozumab followed by a single intravenous infusion of open-label zoledronic acid vs 12 months of placebo followed by a single intravenous infusion of open-label zoledronic acid) from baseline to 24 months on the study endpoints.

Phase 2 Aim 2: A secondary analysis will be performed to determine whether gains achieved in the romosozumab group are maintained through the subsequent 12-month study period using a linear random effects model with the fixed effect being time and the random effect being the intercept. Lack of statistical significance will indicate maintenance (lack of decrease--or increase) of BMD.

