**Atypical femoral fractures.** An atypical femoral fracture is an unusual thigh bone fracture that may occur with little or no trauma. Fractures can occur in both thighs at the same time. Atypical fractures have been reported rarely in patients receiving romosozumab. It is unknown whether the risk of atypical femoral fracture continues after stopping therapy. It can present with new or unusual hip, thigh, or groin pain weeks to months before the fracture is diagnosed. Subjects will be instructed that if they develop any of these symptoms, they should report them to the study doctor and the physician they see for clinical care. Patients presenting with an atypical femur fracture will also be assessed for symptoms and signs of fracture in the contralateral limb.

In clinical studies, after romosozumab discontinuation, BMD returns to approximately baseline levels within 12 months in the absence of follow-up antiresorptive therapy. This is why we propose to follow the 12 months of romosozumab or placebo with a single intravenous infusion of open-label zoledronic acid at the 12-month visit.

The potential effects of romosozumab on the fetus are not known, and therefore precautions against administration to pregnant patients will be instituted. All patients will have pregnancy tests on admission prior to receiving study medication and serial pregnancy tests at every study visit and will be required to use contraception in order to participate in the protocol (unless exempt). Any subject who becomes pregnant during the course of the study and is discharged from participation, will undergo a follow-up study visit. This will include assessment by an MD or NP for study medication related side effects, including hypocalcemia, and measurement of a calcium level if it has not been done clinically.

After patients start taking romosozumab, it is possible that their body may make antibodies to romosozumab. Antibodies to romosozumab have not been associated with changes in the efficacy or safety of romosozumab.

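### Phase 2 Aim 2 treats a non-significant 12-to-24-month change as proof that BMD was maintained, but with at most 20 women that result cannot rule out a partial loss

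*Combined protocol and SAP*

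**What the plan says.** Phase 2, Specific Aim 2 (II. Specific Aims) asks whether one zoledronic acid infusion "will maintain the hypothesized gains in BMD achieved after 12 months of romosozumab administration". It names month-24 lumbar spine BMD as its primary endpoint, with measurements at months 12 and 24.

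The Data Analysis Plan in section VI calls this a secondary analysis. It uses the romosozumab group only, in a "linear random effects model with the fixed effect being time and the random effect being the intercept". The decision rule is: "Lack of statistical significance will indicate maintenance (lack of decrease--or increase) of BMD". The general threshold applies: "Statistical significance will be defined as a two-tailed p-value of" at most 0.05.

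The only sample-size statement, also in section VI, concerns the Phase 1 romosozumab-versus-placebo comparison: "Group sample sizes of 20 (active therapy) to 10 (placebo) for a total N=30 will achieve 80% power". No margin, confidence-interval criterion, power or sample size is given for Phase 2 Aim 2.

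**The concern.** Maintenance is the hypothesis the aim sets out to show, yet the analysis makes it the null hypothesis and accepts it whenever p exceeds 0.05. Absence of significance is not evidence of no change. The rule also works backwards: the fewer women who reach month 24 and the noisier their scans, the more likely it is that maintenance will be declared.

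The question matters in this trial. Section VII (Romosozumab Administration) says that after discontinuation "BMD returns to approximately baseline levels within 12 months in the absence of follow-up antiresorptive therapy", and gives this as the reason for the infusion. A report that the gain was kept would be read as support for the sequence. Under the present rule, that report could be made when part of the gain had been lost.

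A smaller point is that the parenthesis in the rule does not make clear how a significant further increase would be classified. An increase would plainly satisfy the aim as section II words it.

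**Working it through.** **Inputs from the documents**

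- Women in the analysis: at most 20 (Study Procedures, Baseline Visit: "Twenty subjects will be randomized to active romosozumab").
- Two-sided alpha 0.05 (Data Analysis Plan).
- Two measurement times, months 12 and 24 (Specific Aims, Phase 2). With complete data at two visits, the test of time in a random-intercept model is the paired t-test.
- Planned Phase 1 effect: "population mean difference is at least 9% with a standard deviation between groups of 8" percent (section VI).

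**Assumptions**

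- The SD of the within-person 12-to-24-month change is not given. I take 3 to 8 percentage points. The 8% in section VI belongs to the romosozumab-versus-placebo percent change, so it serves here only as the upper end of the range.
- No dropout rate is given. I show n = 20 and, as an illustration, n = 14.

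**Step 1: the plan's own figure.** For a two-sample equal-variance t-test with 20 and 10 women, the noncentrality is 9 / (8 × √(1/20 + 1/10)) = 2.905. With 28 degrees of freedom the critical value is 2.048 and power is 80.06%. The stated 80% is reproduced. It does not carry over to Aim 2, which is a within-arm question.

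**Step 2: chance that a true loss is called maintained.** For a true loss d with n women,

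P(maintained) = F(t*; n−1, d√n/SD) − F(−t*; n−1, d√n/SD),

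where F is the noncentral t distribution function and t* is the 97.5% point of t on n−1 degrees of freedom (2.093 for n = 20, 2.160 for n = 14). For example, with d = 3, n = 20 and SD 5, the noncentrality is 3 × √20 / 5 = 2.683 and P = 28%.

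| SD of change (points) | 3-point loss, n = 20 | 3-point loss, n = 14 | 4.5-point loss, n = 20 | 9-point loss, n = 20 |
|---|---|---|---|---|
| 3 | 1% | 7% | <1% | <0.1% |
| 4 | 11% | 26% | 0.3% | <0.1% |
| 5 | 28% | 45% | 3% | <0.1% |
| 6 | 44% | 59% | 11% | <0.1% |
| 8 | 64% | 74% | 33% | 0.3% |

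The 4.5-point column is half of the planned 9-point difference. At n = 14 and SD 8, a 9-point loss is missed 2.7% of the time. A simulation with 100,000 replicates agreed with the n = 20 figures for a 3-point loss and with both SD 8 figures for a 9-point loss.

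**Step 3: what 20 women can detect.** Setting P(maintained) to 0.50 and to 0.20 and solving for d gives the first two columns. The half-width is t* × SD / √n.

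| SD | Loss missed half the time | Loss detected with 80% power | 95% CI half-width |
|---|---|---|---|
| 3 | 1.4 | 2.0 | 1.4 |
| 5 | 2.3 | 3.3 | 2.3 |
| 8 | 3.7 | 5.3 | 3.7 |

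**Step 4: a margin-based rule.** If maintenance is claimed only when the lower 95% limit lies above −M, a true loss of exactly M is called maintained 2.5% of the time, whatever n and SD are. For an 80% chance of a claim when the true change is zero, M must be at least 2.0 points (SD 3) to 5.3 points (SD 8) at n = 20, and 2.4 to 6.5 points at n = 14. These figures show feasibility; they are not proposed margins.

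**The case against.** The best case for the plan accepts the logical error and disputes its weight.

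- **Rank of the aim.** The Data Analysis Plan calls this a secondary analysis, and the Phase 2 endpoint list gives only the baseline-to-24-month change as primary. The study is a self-described pilot. This is fair: section II and section VI disagree on rank and should be reconciled. A secondary analysis still needs a valid rule.
- **Size of the SD.** The highest miss rates need an SD near 8, a figure that belongs to a different quantity. The Methods give lumbar spine DXA precision as 0.01 g/cm². If that is a per-scan SD and spine BMD is 0.7 to 0.9 g/cm² (an assumption), measurement error in a two-scan difference is √2 × 0.01 / 0.9 = 1.6% to √2 × 0.01 / 0.7 = 2.0%. At SD 2 and n = 20, a 3-point loss would be missed less than 0.1% of the time. That is a floor, because true differences between women add to it. The practical harm could therefore be small, and the documents do not settle it.
- **Attrition.** Nothing in the documents points to n = 14. The drop criteria other than pregnancy cease to apply once the infusion is given, and the Background reports a low drop-out rate in a related study. Withdrawal before the infusion and voluntary drop-out can still bring the number below 20. The n = 20 figures do not depend on this point.

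These arguments limit how large the problem may be. They do not make non-significance evidence of maintenance, and small size is a reason to report an imprecise estimate openly, not to draw a positive conclusion from it.

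**Conclusion.** The concern holds. The rule is wrong as written, and nothing elsewhere in the document repairs it. That conclusion is one of logic and does not depend on any assumed SD.

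The size does depend on the SD. At SD 3 the rule would rarely miss a 3-point loss in 20 women, while at SD 5 to 8 it would miss one in roughly 3 of 10 to 6 of 10 trials. A complete return to baseline after a 9-point gain would almost always be detected, so the exposure is to partial loss reported as maintenance. The Phase 1 primary comparison is unaffected. This should be fixed before the data are unblinded. Confidence is high on the logic and lower on the magnitude.

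**What to change.** Remove the sentence that infers maintenance from non-significance and replace it with the following.

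1. Report the mean percent change in lumbar spine BMD from month 12 to month 24 in the romosozumab group, with its two-sided 95% confidence interval. State whether it comes from the planned random-intercept model and how missing month-24 scans are handled.
2. Claim maintenance only if the lower limit lies above a maximum acceptable loss that is justified and fixed before unblinding.
3. State that an increase counts as maintained.
4. If the interval lies wholly below zero but inside the margin, report both facts: a loss occurred, and it was within the margin.
5. If no margin can be justified, or the lower limit falls below it, give the estimate and interval and make no maintenance claim.

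Also reconcile the primary label in section II with the secondary label in section VI.

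The cost is a few sentences and no new data. The drawback is that the interval may be too wide for any claim: its half-width is about 1.4 (SD 3) to 3.7 points (SD 8) at n = 20, and 1.7 to 4.6 at n = 14. If a margin wide enough to be feasible cannot be defended, the aim should be reported descriptively.

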## **Phase 1 Endpoints:**

### **Primary:**

Change from baseline to 12 months in lumbar spine bone mineral density by dual energy x-ray absorptiometry (DXA).

### **Secondary:**

Change from baseline to 12 months in bone mineral density of hip (total and femoral neck) and radius by DXA.

Change from baseline to 12 months in markers of bone metabolism: CTx, P1NP, Osteocalcin.

### **Exploratory:**

Change from baseline to 12 months in HR-pQCT variables at the tibia and radius—trabecular thickness and spacing, and cortical thickness and porosity; change from baseline to 12 months in ITS variables; change from baseline to 12 months in finite element analysis modeling of bone strength.

## **Phase 2 Endpoints:**

### **Primary:**

Change from baseline to 24 months in lumbar spine BMD.

### **Exploratory:**

Change from baseline to 24 months in markers of bone metabolism: CTx, P1NP, Osteocalcin.

## **VII. Risks and Discomforts**

### **Risks from Procedures**

#### **Blood Sampling:**

Blood sampling is performed in the study and there is always a very minor risk of infection, bruising, or syncope during a blood draw. There is also the discomfort of having one's blood drawn.

#### **Bone Density and Microarchitecture Studies:**

The study involves exposure to radiation from four or five DXA scans, four HR-pQCT scans, and a plain film of the wrist/hand if needed to determine bone age (only in women with primary amenorrhea who have not received estrogen for  $\geq 1$  year). The total radiation dose the subject will receive from all of the scans is 0.19 milliSievert (mSv). This amount of radiation is approximately 6% of the yearly natural background radiation from the earth and the sky (equivalent to 22 days of background radiation). There are no known health risks associated with such a dose.

Subjects will have the option to repeat scans once if there is a technical issue with the machine, which is a rare occurrence. If each scan were repeated at each visit, the total radiation dose the subject would receive from all of the scans would be no more than 0.38 mSv. This amount of radiation is equal to

about 12% of the annual background radiation from the earth and the sky (equivalent to 44 days of background radiation). Subjects have the option to refuse to be re-scanned.

All patients will have pregnancy tests (unless exempt from urine hCG) on admission prior to receiving any radiation. Subjects will also have serial pregnancy tests performed at every study visit. BMD measurements will occur five times, and HR-pQCT of the radius and tibia will be performed four times over the course of 24 months.

## **Risks from Medications**

**Oral calcium** can cause constipation and a metallic taste in the mouth.

**Vitamin D** in the doses being administered does not result in any side effects.

### **Romosozumab Administration:**

Two separate subcutaneous injections are needed to administer the total dose of romosozumab 210 mg. A study clinician will inject two syringes, one after the other, every month for 12 doses in the abdomen, thigh, or upper arm.

Romosozumab 210 mg may cause all, some, or none of the side effects listed below. These side effects can be mild but could also be serious, life-threatening, or even result in death. In addition, it is possible that a subject may experience an allergic reaction that has not been seen before.

Side effects that other people with osteoporosis or bone loss have had in research studies that are thought to have been caused by romosozumab 210 mg are:

Very common side effects (which may affect more than 1 person in 10):

- joint pain
- pain in extremity

Common side effects (which may affect between 1 and 10 people in every 100):

- headache
- muscle spasm
- swelling in extremity
- lack of energy
- neck pain
- trouble sleeping
- tingling or numbness in extremity

Uncommon side effects (which may affect between 1 and 10 people in every 1,000):

- allergic reaction (drug hypersensitivity) (see description below)
- hypocalcemia (see description below)
- heart attack or stroke (in postmenopausal women) (see description below)

Rare side effects (which may affect between 1 and 10 people in every 10,000):

- osteonecrosis of the jaw (ONJ) (see description below)
- unusual thigh bone fracture (atypical femoral fractures) (see description below)

**Hypersensitivity reactions.** Hypersensitivity reactions, including angioedema, erythema multiforme, dermatitis, rash, and urticaria have occurred in romosozumab-treated patients. Subjects will be instructed to call the study doctor immediately if they are concerned about an allergic reaction, and to go immediately to the emergency room if they are concerned about a severe allergic reaction. If an anaphylactic or other clinically significant allergic reaction occurs, romosozumab will be discontinued and the subject will be referred for appropriate treatment.

**Hypocalcemia.** Transient hypocalcemia has been observed in patients receiving romosozumab. Subjects with hypocalcemia, a 25-OH vitamin D level <30 ng/mL, or eGFR <30 ml/min will be excluded from participation in the study. Subjects will be monitored for signs and symptoms of hypocalcemia. All subjects will take daily calcium and vitamin D while in the study.

**Major adverse cardiac event.** In a randomized controlled trial in postmenopausal women, there was a higher rate of major adverse cardiac events (MACE), a composite endpoint of cardiovascular death, nonfatal myocardial infarction and nonfatal stroke, in patients treated with romosozumab compared to those treated with alendronate. Subjects who have had a myocardial infarction or stroke within the preceding year will be excluded from participation in the study.

**Osteonecrosis of the jaw (ONJ).** ONJ is a potentially serious condition that can present as a sore in the mouth through which the jaw bone is sometimes visible. The gum tissue over the bone may heal slowly or not heal at all. How this happens is poorly understood. The symptoms of ONJ include pain or infection in the jaw bone and gums. Subjects will be instructed that if they develop any of these symptoms, they should see their doctor who should examine her mouth to determine if she has ONJ. The risk of developing ONJ is higher in patients who have had tooth removal, gum surgery, infections in the mouth, dental implants or other dental procedures. Subjects will be instructed that it is important that they maintain good oral hygiene and avoid dental procedures immediately before and during their participation in the study, if possible. They will also be instructed that their study doctor and dentist should discuss the benefits and risks of any dental procedure. Additionally, they will be instructed to tell their dentist that they are taking romosozumab before a dental procedure is planned. Although ONJ has been reported rarely in patients receiving romosozumab, we will take all possible precautions to prevent it from occurring, specifically, we will exclude all subjects with an invasive dental procedure within 6 months prior to the baseline visit or planned dental procedure over the next 6 months, and will require all subjects to have had a dental exam within 1 year prior to enrolling in the study.

**Atypical femoral fractures.** An atypical femoral fracture is an unusual thigh bone fracture that may occur with little or no trauma. Fractures can occur in both thighs at the same time. Atypical fractures have been reported rarely in patients receiving romosozumab. It is unknown whether the risk of atypical femoral fracture continues after stopping therapy. It can present with new or unusual hip, thigh, or groin pain weeks to months before the fracture is diagnosed. Subjects will be instructed that if they develop any of these symptoms, they should report them to the study doctor and the physician they see for clinical care. Patients presenting with an atypical femur fracture will also be assessed for symptoms and signs of fracture in the contralateral limb.

In clinical studies, after romosozumab discontinuation, BMD returns to approximately baseline levels within 12 months in the absence of follow-up antiresorptive therapy. This is why we propose to follow the 12 months of romosozumab or placebo with a single intravenous infusion of open-label zoledronic acid at the 12-month visit.

The potential effects of romosozumab on the fetus are not known, and therefore precautions against administration to pregnant patients will be instituted. All patients will have pregnancy tests on admission prior to receiving study medication and serial pregnancy tests at every study visit and will be required to use contraception in order to participate in the protocol (unless exempt). Any subject who becomes pregnant during the course of the study and is discharged from participation, will undergo a follow-up study visit. This will include assessment by an MD or NP for study medication related side effects, including hypocalcemia, and measurement of a calcium level if it has not been done clinically.

After patients start taking romosozumab, it is possible that their body may make antibodies to romosozumab. Antibodies to romosozumab have not been associated with changes in the efficacy or safety of romosozumab.

